7.1.2.12.1 Best Overall Response (RECIST 1.1)

The best overall response is the best response recorded from the start of the study treatment until the end of treatment taking into account any requirement for confirmation. The

patient's best overall response assignment will depend on the findings of both target and non-target disease and will also take into consideration the appearance of new lesions (Table 7).

Table 7 Best Overall Response (RECIST 1.1)

Target Lesions		Non-Target Lesions	
Baseline (Index) and New Measurable Lesions	Baseline Lesions	Unequivocal New Lesions	Overall Response
CR	CR	No	CR
CR	Non-CR/Non-PD	No	PR
CR	NE	No	PR
PR	Non-PD or NE	No	PR
SD	Non-PD or NE	No	SD
Not all evaluated	Non-PD	No	NE
PD	Any	Yes or No	PD
Any	PD	Yes or No	PD
Any	Any	Yes	PD

CR = complete response; NE = not evaluable at a particular time point; PR = partial response; SD = stable disease; PD = progressive disease

© 2019 Pearson Education, Inc. All Rights Reserved. May not be copied, scanned, or duplicated, in whole or in part. Due to electronic rights, some third party content may be suppressed from the eBook and/or eChapter(s). Editorial review has determined that any suppressed content does not materially affect the overall learning experience. Pearson Education, Inc. reserves the right to remove additional content at any time if subsequent rights restrictions require it.

For more information, contact the Office of the Vice President for Research and the Office of the Vice President for Student Affairs.

For more information, contact the Office of the Vice President for Research and Economic Development at [contact] or [contact].

11. **What is the primary purpose of the *Journal of Clinical Endocrinology and Metabolism*?**

Digitized by [contact]

Digitized by [contact]

© 2013 Pearson Education, Inc.

For more information, contact the Office of the Vice President for Research and the Office of the Vice President for Student Affairs.

10 of 10 pages

7.1.2.13.2 Correlative Studies Blood

- [REDACTED]
- [REDACTED]
- [REDACTED]
- [REDACTED]

- **PK Assessment:** Serum will be collected at Cycle 1 Day 1 (pre-dose and end of infusion), at Weeks 3 and 5 (pre-dose only) and at Week 7 (pre-dose and end of infusion). For all subsequent cycles, serum will be collected at Week 7 (pre-dose only) with the exception of Cycle 3 where serum will be collected at Week 7 (pre-dose and end of infusion). Serum will also be collected at end of treatment and at the 90-day post treatment follow up visit.
- **Immunogenicity (ADA) Assessment:** Serum will be collected at Cycle 1 Day 1 (pre-dose only), at Weeks 5 and 7 (pre-dose only). For all subsequent cycles, serum will be collected at Week 7 (pre-dose only). Serum will also be collected at end of treatment and at the 90-day post treatment follow up visit.
- [REDACTED]
- [REDACTED]

7.1.2.14 Safety Laboratory Procedures/Assessments

Details regarding specific laboratory procedures/assessments to be performed in this trial are provided below. The total amount of blood/tissue to be drawn/collected over the course of the trial (from pre-trial to post-trial visits), including approximate blood/tissue volumes drawn/collected by visit and by sample type per subject can be found in the Laboratory Manual.

7.1.2.14.1 Laboratory Safety Evaluations (Hematology, Chemistry and Urinalysis)

Laboratory tests for hematology, chemistry, urinalysis, and others are specified in **Table 9**.

The total amount of blood/tissue to be drawn/collected over the course of the trial (from pre-trial to post-trial visits), including approximate blood/tissue volumes drawn/collected by visit and by sample type per subject can be found in the Laboratory Manual.

Subjects must meet all lab criteria prior to dosing. Laboratory tests can be performed no more than 3 days prior to dosing. If screening laboratory tests are performed within 5 days prior to initial study treatment, they can be used for C1D1 labs. Results must be reviewed by the investigator or qualified designee and found to be acceptable prior to each dose of trial treatment.

Table 9 Laboratory Tests

Hematology	Chemistry	Urinalysis	Other
Hematocrit	Albumin	Blood	Serum β-human chorionic gonadotropin†
Hemoglobin	Alkaline phosphatase	Glucose	(β-hCG)†
Platelet count	Alanine aminotransferase (ALT)	Protein	PT (INR)
WBC (total and differential)	Aspartate aminotransferase (AST)	Specific gravity	aPTT
Red Blood Cell Count	Lactate dehydrogenase (LDH)	Microscopic exam (If abnormal results are noted)	Total triiodothyronine (T3)
Absolute Neutrophil Count	Carbon Dioxide ‡ (CO₂ or bicarbonate)	Urine pregnancy test †	Free tyroxine (T4)
	Creatinine		Thyroid stimulating hormone (TSH)
	Calcium		PK
	Chloride		
	Glucose		Blood for correlative studies
	Potassium		
	Sodium		
	Total Bilirubin		
	Direct Bilirubin (If total bilirubin is elevated above the upper limit of normal)		
	Total protein		
	Blood Urea Nitrogen		

† Perform on women of childbearing potential only. If urine pregnancy results cannot be confirmed as negative, a serum pregnancy test will be required.

‡ If considered standard of care in your region.

7.1.3 Other Procedures

7.1.3.1 Withdrawal/Discontinuation

When a subject discontinues/withdraws prior to trial completion, all applicable activities scheduled for the final trial visit should be performed at the time of discontinuation. Any adverse events which are present at the time of discontinuation/withdrawal should be followed in accordance with the safety requirements outlined in Section 7.2 - Assessing and Recording Adverse Events. Subjects who a) attain a CR or b) complete 12 months of treatment may discontinue treatment with the option of restarting treatment if they meet the criteria specified in Section 7.1.4.2.1. After discontinuing treatment following assessment of CR, these subjects should return to the site for a Safety Follow-up Visit (described in Section 7.1.4.3.1) and then proceed to the Follow-Up Period of the study (described in Section 7.1.5.3.2).

7.1.4 Visit Requirements

Visit requirements are outlined in Section 6.0 - Trial Flow Chart. Specific procedure-related details are provided above in Section 7.1 - Trial Procedures.

7.1.4.1 Screening

Screening period – will start when the first screening evaluation is performed. This does not include signing of Informed Consent or wash out periods. Screening evaluations will be performed within 28 days prior to the first treatment administration, unless otherwise specified.

Informed Consent - each subject must sign a copy of the most current IRB/IEC approved informed consent document. A copy of the signed document will be maintained with the subject's records.

Inclusion/Exclusion Criteria - all inclusion and exclusion criteria will be reviewed by the Investigator or qualified designee to ensure that the subject qualifies for the trial

Medical History/Prior and Concomitant Medications - past or current medical conditions, current medications, medications taken within 28 days of study entry, histological confirmation of cancer, tumor staging (refer to the most current American Joint Committee on Cancer Staging Manual, the fifth edition or higher), and prior cancer therapies and best response(s), if applicable.

Complete physical exam - including baseline ECG and O₂ saturation by pulse oximetry

Pregnancy test - A rapid pregnancy test will be performed for all women of child bearing potential. A positive rapid pregnancy test must be confirmed by serum.

HPV genotyping – specimen collection for confirming HPV+ will be collected for SCCHN subjects, if necessary. Details regarding collection, preparation and shipping specimen can be found in the laboratory manual.

Laboratory Procedures (hematology, chemistry, urinalysis, other) – must be performed within 28 days prior to first dose of study treatment. Screening lab that are done within 5 days of initiating treatment can be used for C1D1 laboratory tests.

Tumor Imaging/Disease Assessment - CT scan or MRI for determination of unidimensional measurements and disease response. Baseline tumor imaging/disease assessment must be performed within 28 days prior to the first dose of study treatment.

Analysis of [REDACTED] – [REDACTED]

[REDACTED]
[REDACTED]
[REDACTED]
[REDACTED]
[REDACTED]

[REDACTED]

Correlative studies: Blood will be collected as indicated in Section [7.1.2.13.2](#).

7.1.4.2 Treatment Period

Subjects will be treated for up to 1 year. Subjects should arrive at the study center early on the days of their scheduled treatment in order to be evaluated, have laboratory specimens collected before treatment commences, allow for infusion timing, and take study prophylactic NSAIDs and antiemetic medication, as described below.

During the time the subjects are at the study site, the infusion line will be left in place to administer parenteral drugs, if necessary. Subjects will remain at the study center for a minimum of [REDACTED] after study treatment for safety observation, and if necessary, treatment of side effects. Subjects may receive NSAIDs every 4 hours and antiemetics every 8 hours after receiving each ADXS11-001 infusion, as needed.

Adverse Event Monitoring - the Investigator or qualified designee will assess each subject to evaluate for potential new or worsening AEs as specified in the Schedule of Events and more frequently if clinically indicated. Adverse events will be graded and recorded throughout the study and follow-up according to NCI CTCAE v 4.03. Toxicities will be characterized in terms regarding seriousness, causality, toxicity grading, and action taken with regard to trial treatment.

Physical Examination - evaluation by body system.

Vital Signs - blood pressure, pulse rate, respiratory rate, and temperature will be checked and recorded prior to any infusions and [REDACTED] following the ADXS11-001 infusion. Height and weight will be measured at screening, and weight will be measured pre-dose at every visit.

ECOG Performance Status - according to ECOG criteria.

Laboratory Procedures (hematology, chemistry, urinalysis, other) – must be performed no more than 3 days prior to dosing. Screening lab that are done within 5 days of initiating treatment can be used for C1D1 laboratory tests. Please see Section 7.1.2.14.1 for details.

Prophylactic Medications – Subjects will receive a dose of NSAIDS (e.g. naproxen or ibuprofen) and antiemetics (e.g. promethazine or ondansetron) [REDACTED] prior to all ADXS11-001 infusions. Subjects should continue to receive NSAIDS, every 4 hours as needed, following the ADXS11-001 infusions.

PO Antibiotics with Instructions – Subjects will receive a 3 day course of one of the following oral antibiotics (amoxicillin, ampicillin, ciprofloxacin, erythromycin, gentamycin, penicillin, trimethroprim/sulfamethoxazole, or vancomycin), to be started on **Day 4** (72 hours) after each ADXS11-001 infusion. ADXS11-001 is resistant to both streptomycin and chloramphenicol. In the event a subject experiences a persistent fever present at 72 hours after receiving ADXS11-001, the oral regimen will be replaced by IV administration

Correlative studies: Blood will be collected as indicated in Section 7.1.2.13.2.

Analysis of [REDACTED]
[REDACTED]

Tumor Imaging/Disease Assessment - CT scan or MRI for determination of unidimensional measurements and disease response. Imaging studies and tumor assessments will be performed every 8 weeks starting with Day 1 of Cycle 2.

Pregnancy test - A rapid pregnancy test will be performed within 72 hours of each treatment administration (combination or monotherapy) for all women of child bearing potential prior to treatment. A positive rapid pregnancy test must be confirmed, prior to dosing, by serum pregnancy test (minimum sensitivity 25 IU/L or equivalent units of β HCG).

7.1.4.2.1 Re-Treatment Period

Subjects who attain a CR during treatment or complete 1 year of treatment may discontinue treatment with the option of an additional 1 year of treatment at the same treatment they were previously assigned if:

- during the first 12 months of the subject's follow up period (Section [7.1.4.3.2](#)), disease progression is noted
- other subjects are still currently being treated
- subject still meets eligibility criteria
- sponsor and investigator are in agreement

Subjects will be re-consented and must meet all baseline inclusion exclusion to receive subsequent therapy. Eligibility criteria will only be evaluated prior to retreatment and not prior to every subsequent cycle.

Retreatment Visit schedule is outlined in Section [6.5](#) – Retreatment Study Flow. Re-baseline evaluations will be performed within 28 days prior to the first retreatment administration.

7.1.4.3 Post-Treatment Visits

7.1.4.3.1 Safety Follow-Up Visit

The mandatory Safety Follow-Up Visit should be conducted approximately 30 days (± 5 days) after the last dose of trial treatment or before the initiation of a new anti-cancer treatment, whichever comes first. All AEs that occur prior to the Safety Follow-Up Visit should be recorded. Subjects with an AE of Grade > 1 will be followed until the resolution of the AE to Grade 0-1 or until the beginning of a new anti-neoplastic therapy, whichever occurs first. SAEs that occur within 90 days of the end of treatment or before initiation of a new anti-cancer treatment should also be followed and recorded.

7.1.4.3.2 Follow-up Visits

90 day post treatment visit – Blood will be collected for PK/ADA/ [REDACTED] markers on all subjects assigned to receive MEDI4736 monotherapy or Combination therapy.

8-week post treatment visit - Subjects who discontinue trial treatment or retreatment for a reason other than disease progression should be assessed every 8 weeks (\pm 1 week) by radiologic imaging to monitor disease status for up to three years. Every effort should be made to collect information regarding disease status until the start of new anti-neoplastic therapy, disease progression, death, end of the study or if the subject begins retreatment as detailed in Section [7.1.4.2.1](#).

Subjects who are in the follow up phase and experience disease progression may have the option to be retreated, after discussion with the sponsor. Details are provided in Section [6.5](#) –Retreatment Flow Chart and Section [7.1.4.2.1](#)– Retreatment Period

7.2 Assessing and Recording Adverse Events

An adverse event is defined as any untoward medical occurrence in a patient or clinical investigation subject administered a pharmaceutical product and which does not necessarily have to have a causal relationship with this treatment. An adverse event can therefore be any unfavorable and unintended sign, symptom, or disease temporally associated with the use of a medicinal product or protocol-specified procedure, whether or not considered related to the medicinal product or protocol-specified procedure. Any worsening (i.e., any clinically significant adverse change in frequency and/or intensity) of a preexisting condition that is temporally associated with the use of the Sponsor's product, is also an adverse event.

The Sponsor's product includes any pharmaceutical product, biological product, device, diagnostic agent or protocol-specified procedure, whether investigational (including placebo or active comparator medication) or marketed, manufactured by, licensed by, provided by or distributed by Advaxis for human use.

Adverse events may occur during the course of the use of Advaxis' product in clinical trials or within the follow-up period specified by the protocol, or prescribed in clinical practice, from overdose (whether accidental or intentional), from abuse and from withdrawal.

Adverse events may also occur in screened subjects during any pre-allocation baseline period as a result of a protocol-specified intervention, including washout or discontinuation of usual therapy, diet, placebo treatment or a procedure.

All adverse events will be recorded from the time the consent form is signed through 30 days following cessation of treatment and at each examination on the Adverse Event case report forms/worksheets. The reporting timeframe for adverse events meeting any serious criteria is described in Section [7.2.3.1](#).

Adverse events will not be collected for subjects during the pre-screening period (for determination of archival tissue status) as long as that subject has not undergone any protocol-specified procedure or intervention. If the subject requires a blood draw, fresh tumor biopsy etc., the subject is first required to provide consent to the main study and AEs will be captured according to guidelines for standard AE reporting.

7.2.1 Definition and Reporting of an Overdose

For purposes of this trial, an overdose will be defined as any dose exceeding 20% over the prescribed dose of ADXS11-001 or MEDI4736. No specific information is available on the treatment of overdose. In the event of overdose, the subject should be observed closely for signs of toxicity. Appropriate supportive treatment should be provided if clinically indicated.

If an adverse event(s) is associated with ("results from") the overdose of the study drug(s), the adverse event(s) is reported as a serious adverse event, even if no other seriousness criteria are met.

If a dose of Advaxis' product meeting the protocol definition of overdose is taken without any associated clinical symptoms or abnormal laboratory results, the overdose is reported as

a non-serious Event of Clinical Interest (ECI), using the terminology “accidental or intentional overdose without adverse effect.”

All reports of overdose with and without an adverse event must be reported within 24 hours to the Sponsor and within 2 working days hours to inVentiv Health Clinical Pharmacovigilance (Attn: iHC SAE Reporting; [contact] or email: [contact]).

7.2.2 Reporting of Pregnancy and Lactation to the Sponsor

Although pregnancy and lactation are not considered adverse events, it is the responsibility of investigators or their designees to report any pregnancy or lactation in a subject (spontaneously reported to them), including the pregnancy of a male subject's female partner that occurs during the trial or within 120 days of completing the trial completing the trial, or 30 days following cessation of treatment if the subject initiates new anticancer therapy, whichever is earlier. All subjects and female partners of male subjects who become pregnant must be followed to the completion/termination of the pregnancy. Pregnancy outcomes of spontaneous abortion, missed abortion, benign hydatidiform mole, blighted ovum, fetal death, intrauterine death, miscarriage and stillbirth must be reported as serious events (Important Medical Events). If the pregnancy continues to term, the outcome (health of infant) must also be reported.

Such events must be reported within 24 hours of awareness to inVentiv Health Clinical Pharmacovigilance (Attn: iHC SAE Reporting; [contact] or email: [contact])

7.2.3 Immediate Reporting of Adverse Events to the Sponsor

7.2.3.1 Serious Adverse Events

A serious adverse event is any adverse event occurring at any dose or during any use of Advaxis' product that:

- Results in death;

- Is life threatening;
- Results in persistent or significant disability/incapacity;
- Results in or prolongs an existing inpatient hospitalization;
- Is a congenital anomaly/birth defect;
- Is a new cancer (that is not a condition of the study);
- Is associated with an overdose;
- Is another important medical event

Progression of the cancer under study is not considered an adverse event unless it results in hospitalization or death.

Any serious adverse event, or follow up to a serious adverse event, including death due to any cause other than progression of the cancer under study that occurs to any subject from the time the consent is signed through 90 days following cessation of treatment, or the initiation of new anti-cancer therapy, whichever is earlier, whether or not related to Advaxis' product, must be reported within 24 hours to the Sponsor at inVentiv Health Clinical Pharmacovigilance (Attn: iHC SAE Reporting; [contact] or email: [contact]).

Non-serious Events of Clinical Interest will be forwarded to inVentiv Health Clinical Pharmacovigilance (Attn: iHC SAE Reporting; [contact] or email: [contact]) and will be handled in the same manner as SAEs.

Additionally, any serious adverse event, considered by an investigator who is a qualified physician to be related to Advaxis' product that is brought to the attention of the investigator at any time outside of the time period specified in the previous paragraph also must be reported immediately to the Sponsor.

SAE reports and any other relevant safety information are to be forwarded to inVentiv Health Clinical Pharmacovigilance (Attn: iHC SAE Reporting; [contact] or email: [contact]).

A copy of all 15 Day Reports and Annual Progress Reports is submitted as required by FDA, European Union (EU), Pharmaceutical and Medical Devices agency (PMDA) or other local regulators. Investigators will cross reference this submission according to local regulations to the Advaxis Investigational Compound Number (IND, CSA, etc.) at the time of submission. Additionally, investigators will submit a copy of these reports to inVentiv Health Clinical Pharmacovigilance (Attn: iHC SAE Reporting; [contact] or email: [contact]) at the time of submission to FDA.

All subjects with serious adverse events must be followed up for outcome.

7.2.3.2 Events of Clinical Interest

Selected non-serious and serious adverse events are also known as Events of Clinical Interest (ECI) and must be recorded as such on the Adverse Event case report forms/worksheets and reported within 24 hours to the Sponsor and within 2 working days to inVentiv Health Clinical Pharmacovigilance (Attn: iHC SAE Reporting; [contact] or email: [contact]).

Events of clinical interest for this trial include:

1. Pneumonitis - Pneumonitis has been reported in association with use of anti-PD-L1/anti-PD-1 antibodies [36]. Initial work-up should include a high-resolution CT scan, ruling out infection, and pulse oximetry. Pulmonary consultation is recommended.
2. Hypersensitivity Reactions - Hypersensitivity reactions as well as infusion-related reactions have been reported with anti-PD-L1 and anti-PD-1 therapy [36]. As with the administration of any foreign protein and/or other biologic agents, reactions following the infusion of mAbs can be caused by various mechanisms, including

acute anaphylactic (IgE-mediated) and anaphylactoid reactions against the mAb, and serum sickness. Acute allergic reactions may occur, may be severe, and may result in death. Acute allergic reactions may include hypotension, dyspnea, cyanosis, respiratory failure, urticaria, pruritis, angioedema, hypotonia, arthralgia, bronchospasm, wheeze, cough, dizziness, fatigue, headache, hypertension, myalgia, vomiting and unresponsiveness.

- Subjects with Grade 1 and 2 hypersensitivity (including anaphylactic reaction) and infusion-related reactions should be treated according to standard medical practices. If a subject experiences a grade 3 or 4 infusion reaction, the infusion will be discontinued immediately, and no subsequent infusions may be given.
- A grade 3 or 4 infusion reaction will require immediate treatment, including the use of epinephrine, bronchodilators, and/or glucocorticoids for symptomatic bronchospasm; IV fluids and/or pressors for hypotension; and immediate and permanent discontinuation of study drug(s) with appropriate supportive care.

3. Hepatic Function Abnormalities (Hepatotoxicity) - Increased transaminases have been reported during treatment with anti-PD-L1 [\[36\]](#).

Hepatic function abnormality is defined as any increase in ALT or AST to greater than $3 \times \text{ULN}$ **and concurrent** increase in bilirubin to greater than $2 \times \text{ULN}$ (i.e., Hy's Law cases). Concurrent findings are those that derive from a single blood draw or from separate blood draws taken within 8 days of each other. Follow-up investigations and inquiries will be initiated promptly by the investigational site to determine whether the findings are reproducible and/or whether there is objective evidence that clearly supports causation by a disease (e.g., cholelithiasis and bile duct obstruction with distended gallbladder) or an agent other than the investigational product(s).

If an event of hepatic function abnormality is considered to be related to a pre-existing condition and does not represent a worsening of this condition and/or is considered to be within the range of normal physiological fluctuation for the subject, the event does not meet the definition of an AE and does not need to be recorded as such.

If the underlying diagnosis for the hepatic function abnormality is known (including progression of pre-existing disease such as primary or metastatic malignancy), the diagnosis should be recorded as an AE/SAE.

In the event a subject develops any of the following AEs, a detailed narrative of the event should be reported as an ECI to the Sponsor within 24 hours:

- Grade ≥ 3 diarrhea
- Grade ≥ 3 colitis
- Grade ≥ 2 pneumonitis
- Grade ≥ 3 hypo- or hyperthyroidism

Subjects should be assessed for possible ECIs prior to each dose. Lab results should be evaluated and subjects should be asked for signs and symptoms suggestive of an immune-related event. Subjects who develop an ECI thought to be immune-related should have additional testing to rule out other etiologic causes. If lab results or symptoms indicate a possible immune-related ECI, then additional testing should be performed to rule out other etiologic causes. If no other cause is found, then it is assumed to be immune-related.

ECIs that occur in any subject from the date of first dose through 90 days following cessation of treatment, or the initiation of a new anticancer therapy, whichever is earlier, whether or not related to the Advaxis' product, must be reported within 24 hours to the Sponsor.

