4.2.4.2 Safety Endpoints

The primary safety objective of this trial is to characterize the safety and tolerability of ADXS11-001 alone, MEDI4736 alone, and ADXS11-001 in combination with MEDI4736 in subjects with previously treated locally advanced or metastatic SSCHN or cervical cancer. The primary safety analysis will be based on subjects who experience toxicities as defined by NCI CTCAE v 4.03. Safety will be assessed by quantifying the toxicities and grades, including SAEs and events of clinical interest (ECI) experienced by subjects who have

received ADXS11-001, MEDI4736, or ADXS11-001 + MEDI4736 combination therapy. The attribution to drug, time-of-onset, duration of the event, its resolution, and any concomitant medications administered will be recorded. AEs will be analyzed including but not limited to all AEs, SAEs, fatal AEs, and laboratory changes.

4.2.4.3 [REDACTED]

[REDACTED]

[REDACTED]

[REDACTED]

[REDACTED]

[REDACTED]

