Platelets	$\geq 75,000 / \text{mcL}$
Hemoglobin	$\geq 9 \text{ g/dL}$ or $\geq 5.6 \text{ mmol/L}$
Renal	
Serum creatinine OR Measured or calculated ^a creatinine clearance (GFR can also be used in place of creatinine or CrCl)	$\leq 1.5 \times$ upper limit of normal (ULN) OR $\geq 50 \text{ mL/min}$ for subject with creatinine levels $> 1.5 \times$ institutional ULN
Hepatic	
Serum total bilirubin	$\leq 1.5 \times$ ULN OR Direct bilirubin \leq ULN for subjects with total bilirubin levels $> 1.5 \text{ ULN}$
AST (SGOT) and ALT (SGPT)	$\leq 2.5 \times$ ULN OR $\leq 5 \times$ ULN for subjects with liver metastases
Coagulation	
International Normalized Ratio (INR) or Prothrombin Time (PT)	$\leq 1.5 \times$ ULN unless subject is receiving anticoagulant therapy as long as PT or INR is within therapeutic range of intended use of anticoagulants
Activated Partial Thromboplastin Time (aPTT)	$\leq 1.5 \times$ ULN unless subject is receiving anticoagulant therapy as long as aPTT is within therapeutic range of intended use of anticoagulants
^a Creatinine clearance should be calculated per institutional standard.	

8. Female subjects of childbearing potential (not surgically sterilized or not free from menses for > 1 year):
 - a. must have a negative urine or serum pregnancy test result within 72 hours prior to receiving the first dose of study medication. If the urine test is positive or cannot be confirmed as negative, a serum pregnancy test will be required.
 - b. must be willing to use 2 methods of birth control through 120 days after the last dose of study treatment (Section 5.7.2).
9. Male subjects must agree to use an adequate method of contraception starting with the first dose of study treatment through 120 days after the last dose of study therapy.

10. Must have a washout period of at least **14** days from completing prior standard of care therapy to the initiation of study therapy. For subjects who have been treated with either prior investigational therapy, including, but not limited to anti-PD-1, anti-PD-L1 or CTLA4 therapy, a washout period of **28** days is required*. (* *If a subject received a therapy where delayed toxicity is a concern or expected (e.g., skin reaction with RT or mucositis with 5FU) then additional wash out should be considered after discussion with the medical monitor.*)

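### The hepatic ECI is defined by laboratory thresholds, but an open-label judgement with no numeric criterion can take a threshold crossing out of the AE set, and so out of the ECI count and 24-hour reporting

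*Combined protocol and SAP*

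**What the plan says.** Section 7.2.3.2 gives a purely numerical definition. "Hepatic function abnormality is defined as any increase in ALT or AST to greater than" 3x ULN, together with a concurrent rise in bilirubin above 2x ULN, is the hepatic ECI, and the text equates these with Hy's Law cases. Concurrent means one blood draw, or draws within 8 days of each other.

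The exemption follows. Its condition is worded as "considered to be related to a pre-existing condition and does not represent a worsening of this condition and/or is considered to be within the range", the sentence then naming ordinary variation in that subject. When this condition holds, "the event does not meet the definition of an AE and does not need to be recorded as such". The next sentence says that a known underlying diagnosis, "including progression of pre-existing disease such as primary or metastatic malignancy", is to be recorded as an AE/SAE.

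Four other provisions bear on this:

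- Section 7.2.3.2 opens by describing ECIs as selected adverse events. It closes by requiring ECIs to be reported within 24 hours, from first dose to 90 days after treatment "or the initiation of a new anticancer therapy, whichever is earlier, whether or not related to the" sponsor's product.
- Section 4.2.4.2 says safety will be assessed by "quantifying the toxicities and grades, including SAEs and events of clinical interest (ECI) experienced by subjects" on each treatment. It also lists laboratory changes among the analyses.
- Section 7.2.3.1 states: "Progression of the cancer under study is not considered an adverse event unless it results in hospitalization or death".
- Section 5.2.3 makes the trial open label, and Section 8.2 says there is no external data safety monitoring committee.

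**The concern.** The definition is objective, but the exemption placed directly after it is not. It turns on what the event is considered to be, with no numeric limit, reference value or second reader. Because the two branches are joined by and/or, the fluctuation judgement is enough on its own. An event that is not an AE cannot be an ECI, so an exempted crossing disappears from a count that Section 4.2.4.2 names as a safety outcome and is not sent to the sponsor within 24 hours. Treatment is known when the judgement is made, so the count of the main liver signal could depend on how willing sites are to attribute a result to background disease in each arm.

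A second question arises when the cause is known. The section asks for the diagnosis to be recorded but does not say whether the hepatic ECI record stays. For progression, two neighbouring sections also give different answers on whether there is an AE at all.

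**Working it through.** The plan gives no event rate, power or sample-size figure that depends on this rule, so there is no document figure to reproduce. The check compares passages and entry limits; the arithmetic at the end is illustrative.

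**1. Can a subject already be above both thresholds at entry?** Inputs from Table 1 (Section 5.1.1): AST/ALT up to 2.5x ULN, or up to 5x ULN with liver metastases; total bilirubin up to 1.5x ULN, or direct bilirubin at or below "ULN for subjects with total bilirubin levels" above 1.5x ULN. ECI thresholds: above 3x and above 2x.

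| Entry route | AST/ALT at entry | Total bilirubin at entry | Already above both? |
|---|---|---|---|
| Neither exception | up to 2.5x | up to 1.5x | No, on both components |
| Liver metastases only | up to 5x | up to 1.5x | No, bilirubin is below 2x |
| Direct-bilirubin route only | up to 2.5x | may exceed 2x | No, AST/ALT is below 3x |
| Both exceptions | up to 5x | may exceed 2x | Possible |

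The smallest rise needed from the standard limits is 3/2.5 = 1.2-fold for AST/ALT and 2/1.5 = 1.33-fold for bilirubin. Outside the last row, a crossing means that at least one component has risen above its entry limit. The definition itself also speaks of an increase to above the thresholds, so an unchanged baseline abnormality arguably never qualifies. The no-worsening branch therefore has little legitimate work to do. The fluctuation branch has no numeric bound and can be applied to any subject.

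**2. What else captures the result?** ALT, AST and total bilirubin are in Table 9, and Section 7.1.2.14.1 requires results to be reviewed before each dose. Laboratory changes are analysed (Section 4.2.4.2). Neither that section nor Section 8.1 specifies a table of concurrent AST/ALT >3x and bilirubin >2x. The flow charts in Sections 6.1 to 6.4 schedule chemistry up to the discontinuation visit and not after, while ECIs are collected for 90 days. In that window the flow charts leave AE/ECI reporting as the only capture route.

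**3. Progression.** Section 7.2.3.2 has progression, as the underlying diagnosis, recorded as an AE/SAE. Section 7.2.3.1 makes it an AE only when it leads to hospitalization or death. The two differ for a hepatic abnormality caused by progression with neither outcome.

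**4. Illustration.** The 48 Part B subjects at 1:1:2 give 12, 12 and 24. In the combination arm, one recorded case is 1/24 = 4.2% (exact 95% CI 0.1% to 21.1%). If that case is exempted, it is 0/24 = 0%, with an upper limit of 1 − 0.025^(1/24) = 14.2%.

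Let p be an assumed true rate of crossings and f an assumed share exempted. The chance of recording at least one is 1 − [1 − p(1 − f)]^24.

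| Assumed p | f = 0 | f = 0.5 |
|---|---|---|
| 2% | 38.4% | 21.4% |
| 5% | 70.8% | 45.5% |
| 10% | 92.0% | 70.8% |

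Neither p nor f comes from the documents.

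**The case against.** The strongest reply is that the result is not lost. The exemption removes the duty to record the event as an AE. Scheduled laboratory values are still drawn, reviewed before dosing and analysed, and the internal team in Section 8.2 reviews individual data. A reader who infers that a Hy's Law result may go unrecorded goes further than the text. That stands, and it limits the point to the ECI count and the 24-hour report. It is not a full answer, because no combined-threshold table is planned and a later table does not restore prompt reporting.

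A reader might also see a flat contradiction with the duty to report ECIs regardless of relation to the product. There is tension only. That duty covers events that are already ECIs, whereas the exemption asks earlier whether there is an AE. Its no-worsening condition matches the general definition in Section 7.2, under which worsening of a pre-existing condition is an AE.

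It is tempting to read the known-diagnosis sentence as replacing the ECI record with the diagnosis. The text does not say so; it is silent on whether the ECI record stays.

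Finally, a reader might infer that a Part A dose-limiting toxicity could vanish and change escalation. Section 5.2.1.2 does not support this. Its item 6 is a separate laboratory criterion that depends on relatedness to the combination, not on AE recording under Section 7.2.3.2. An event judged related could hardly also be exempted as background; if attributed to background, it would fail item 6 with or without the exemption.

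Two further points are fair. A value above the entry limit is not identical to worsening of the underlying condition. And the section does ask for prompt follow-up on reproducibility and for objective evidence of another cause. But the exemption is not tied to that evidence; it needs only that the event be considered benign.

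**Conclusion.** The concern holds as a gap in the recording rule. An event meeting the protocol's own laboratory definition can fall outside the AE set, and so outside the ECI count and 24-hour reporting, on an open-label judgement without a numeric criterion. Table 1 shows that the pre-existing-condition branch is rarely justified: only a subject using both entry exceptions can start above both thresholds. The separate inconsistency on progression between Sections 7.2.3.1 and 7.2.3.2 is real and must be reconciled.

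The documents do not support a reading in which results are lost, the ECI record is replaced by the diagnosis, or dose escalation is affected. The size is unknown because no event frequency is given. The 4.2% to 0% change and the detection probabilities only show how sensitive a count in 24 subjects is, and the two exact intervals overlap heavily. The change should be made because it is cheap and frees the count of the main liver signal from a discretionary step.

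**What to change.** 1. In Section 7.2.3.2, replace the exemption with a rule that every crossing of the hepatic thresholds is recorded and reported as an ECI, with relatedness and any alternative cause documented. Allow an exception only where baseline values already met the definition and have not risen.
2. State that the ECI record stays when an underlying diagnosis is also recorded.
3. Reconcile the sentences on progression in Sections 7.2.3.1 and 7.2.3.2 so that sites have one rule.
4. Add to Section 8.1 a table by treatment arm of concurrent ALT or AST >3x ULN and bilirubin >2x ULN (same draw or within 8 days), derived from the laboratory data and independent of AE judgement. Note beside it that the flow charts schedule no chemistry after discontinuation, so the table alone cannot cover the 90-day ECI window.

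The cost is a few sentences, one table and a few more ECI forms. The reported hepatic ECI rate may be slightly higher, because crossings caused by background disease or progression will be counted with their cause shown.
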